2.3 Calcitonin ≥ 10 and <50 ng/L

Action: The subject can continue in the trial on trial product. Continue sampling of calcitonin according to the protocol.

If the subject is a screen failure, or if the value is from the last sample taken in the trial, the subject should be referred to a thyroid specialist for further evaluation.

Background: Calcitonin values from 20-50 ng/L were found in up to 1% of subjects of the population of 5817 patients with thyroid nodular disease.¹ The predictive value of a C-cell anomaly for this calcitonin level was 8.3%. However, the likelihood of having a medullary carcinoma >1 cm with calcitonin in this range is extremely low.

For calcitonin values 10-20 ng/L Costante et al¹ identified 216 (3.7%) patients. One patient out of the 216 had a subsequent basal (unstimulated) calcitonin of 33 ng/L, and had C-cell hyperplasia at surgery. Two other studies used a cut-off of CT > 10 ng/L to screen for C-cell disease, but they do not provide sufficient information on patients with basal CT >10 and <20 ng/L to allow conclusions^{2,3}

3 References

Liraglutide 3.0 mg
Trial ID: NN8022-4272
Clinical Trial Report
Appendix 16.1.1

~~CONFIDENTIAL~~

Date:
Version:
Status:

19 February 2019 | **Novo Nordisk**
1.0
Final

Global and country key Novo Nordisk staff

Attachments I and II (if applicable) to the protocol are located in the Trial Master File.

Content: Global key staff and Country key staff

Protocol Amendment
Trial ID: NN8022-4272
UTN: U1111-1177-4903
EudraCT No.: 2015-005619-33

~~CONFIDENTIAL~~

Date:
Version:
Status:
Page:

14 November 2016
2.0
Final
1 of 4

Novo Nordisk

Protocol Amendment
no 1
to Protocol, final version 4.0
dated 14 September 2016

Trial ID: NN8022-4272

SCALE™ Insulin
Effect and safety of liraglutide 3.0 mg in subjects with overweight or obesity and type 2
diabetes mellitus treated with basal insulin

Trial phase: 3b

Applicable to all countries

Amendment originator:

This ~~confidential~~ document is the property of Novo Nordisk. ~~No unpublished information contained herein may be disclosed without prior written approval from Novo Nordisk. Access to this document must be restricted to relevant parties.~~

Table of Contents

	Page
Table of Contents.....	2
1 Introduction including rationale for the protocol amendment.....	3
2 Changes.....	3
2.1 Section 2 Flow chart.....	3
2.2 Section 5.3.2.2 Treatment with insulin throughout the trial.....	3
2.3 Section 8.2.5 Concomitant medication.....	3
2.4 Section 8.3.9 Insulin dose.....	3
2.5 Section 8.5.2 Laboratory assessments for safety.....	4

1 Introduction including rationale for the protocol amendment

Rationale for the changes:

- Addition of bicarbonate as a part of the biochemistry laboratory assessment. The FDA has requested that bicarbonate is added as a routine laboratory test in trials where sodium-glucose cotransporter-2 (SGLT2) inhibitors are used as background medication, because SGLT2-inhibitors have been associated with a risk for metabolic acidosis. Hence, serum bicarbonate assay has been included to collect additional safety information in alignment with other Novo Nordisk trials where trial product is add-on to an SGLT2 inhibitor. There is no safety risk for those subjects who do not have the bicarbonate assay performed during their treatment.
- Inconsistent wording in reporting of insulin dose and transcription of insulin dose to eCRF.
- Discrepancy regarding the time period of an eye examination performed prior to randomisation.

In this protocol amendment:

- Any new text is written *in italics*.
- Any text deleted from the protocol is written using ~~strike through~~.

2 Changes

2.1 Section 2 Flow chart

³Only if not available within last 90 days before ~~screening~~ randomisation

2.2 Section 5.3.2.2 Treatment with insulin throughout the trial

~~The insulin dose adjustments recorded in the diabetes diary, must be entered in the electronic case report form (eCRF).~~

2.3 Section 8.2.5 Concomitant medication

The products described as NIMP (see Section 5.3.2) are also recorded as concomitant medication in the eCRF. However the adjustments of insulin doses performed during the trial will be recorded in the designated ~~form~~ *diabetes diary* and these must be assessed by the investigator.

2.4 Section 8.3.9 Insulin dose

Subjects will be instructed in how to record the insulin use in the provided diabetes diary *and* the investigator should review the subject's insulin dose. ~~as specified in Section 8.1.~~ *From visit 2 and until but not including the follow-up visit, the investigator must record the subject's basal and bolus (if applicable) daily injected doses, respectively, prior to each scheduled visit in the eCRF. Results of the subject's SMPG measurements should be noted in the diabetes diary and total daily injected dose of basal/bolus insulin prior to each contact will be transcribed into the eCRF and*

~~based on these, dose adjustment guidance will be provided. All adjustments of insulin dose level will be captured in the eCRF. From visit 2 and until follow up, the investigator should record the subject's total daily injected dose of insulin (basal/bolus) prior to each visit in the eCRF.~~

2.5 Section 8.5.2 Laboratory assessments for safety

Biochemistry

Blood samples for biochemistry must be collected at the specified visits (see Section 2).

- Creatinine
- Urea (blood urea nitrogen)
- Uric acid
- Alanine aminotransaminase (ALT)
- Aspartate aminotransferase (AST)
- Alkaline phosphatase (ALP)
- Albumin
- Amylase
- *Bicarbonate*
- Lipase
- Sodium
- Potassium
- Calcium, total
- Calcitonin (please refer to Appendix A for actions to be taken if calcitonin is ≥ 10 ng/L)
- TSH*
- Bilirubin, total (TBL)
- hs-CRP**
- GFR, estimated

*If TSH levels are out of normal range, the investigator must perform additional testing:

- Total and free T3 and T4 and Free Thyroid Index
- Thyroid peroxidase antibodies

**hs-CRP is only measured at Visit 2 and Visit 24.

Protocol Amendment no. 2
Trial ID: NN8022-4272
UTN: U1111-1177-4903
EudraCT No.: 2015-005619-33

~~CONFIDENTIAL~~

Date:
Version:
Status:
Page:

15 March 2017 | **Novo Nordisk**
1.0
Final
1 of 5

Protocol Amendment
no 2
to Protocol, final version 6.0
dated 15 November 2016

Trial ID: NN8022-4272

SCALE™ Insulin
Effect and safety of liraglutide 3.0 mg in subjects with overweight or obesity and type 2
diabetes mellitus treated with basal insulin

Trial phase: 3b

Applicable to all countries

Amendment originator:

This ~~confidential~~ document is the property of Novo Nordisk. ~~No unpublished information contained herein may be disclosed without prior written approval from Novo Nordisk. Access to this document must be restricted to relevant parties.~~

Table of Contents

	Page
Table of Contents.....	2
1 Introduction including rationale for the protocol amendment.....	3
2 Changes.....	3
2.1 Section 1 Summary.....	3
2.2 Section 4.1 Objectives.....	4
2.3 Section 5.1 Type of trial.....	5
2.4 Section 5.3.2.1 Oral antidiabetic medication.....	5
2.5 Section 5.3.2.2 Treatment with insulin throughout the trial.....	5
2.6 Section 6.2 Inclusion criteria.....	5

1 Introduction including rationale for the protocol amendment

Rationale for the changes:

- Inclusion criterion 3 updated to allow for two additional oral antidiabetic drug (OAD) classes (alpha glucosidase inhibitors and glinides) which are currently not permitted. There are no medical reasons for not including them.
- Inclusion criterion 4 updated to allow subjects to continue on their standard insulin treatment. Currently the inclusion criterion states that subjects should be treated with any basal insulin according to its label. However, some subjects with type 2 diabetes mellitus and obesity are using insulin glargine twice daily (BID), due to the high dose based on the subjects' high body weight.

In this protocol amendment:

- Any new text is written *in italics*.
- Any text deleted from the protocol is written using ~~strike through~~.

2 Changes

2.1 Section 1 Summary

Objectives and endpoints

Primary objective

To confirm superiority of liraglutide 3.0 mg vs. placebo, as an adjunct to a reduced-calorie diet and increased physical activity, on weight loss effectiveness in subjects with overweight or obesity and type 2 diabetes mellitus (T2DM) treated with a basal insulin and up to 2 oral antidiabetic (OAD) medications (metformin, glitazone, SGLT-2 inhibitor, *alpha glucosidase inhibitor*, *glinide* or sulphonylurea).

Secondary objectives

To establish the effects of liraglutide 3.0 mg vs. placebo, as an adjunct to a reduced-calorie diet and increased physical activity, on relevant efficacy endpoints in subjects with overweight or obesity and T2DM treated with basal insulin and up to 2 OADs (metformin, glitazone, SGLT-2 inhibitor, *alpha glucosidase inhibitor*, *glinide* or sulphonylurea)

To establish the safety and tolerability of liraglutide 3.0 mg vs. placebo, as an adjunct to a reduced-calorie diet and increased physical activity, in subjects with overweight or obesity and T2DM treated with basal insulin and up to 2 OADs (metformin, glitazone, SGLT-2 inhibitor, *alpha glucosidase inhibitor*, *glinide* or sulphonylurea)

Trial design

This is a 56-week randomised, double-blind, multi-national, multi-centre, placebo-controlled and two-armed trial in subjects with overweight or obesity and T2DM treated with basal insulin and up to two OADs (metformin, glitazone, SGLT-2 inhibitor, *alpha glucosidase inhibitor*, *glinide* or sulphonylurea).

Key inclusion criteria

1. Informed consent obtained before any trial-related activities. Trial-related activities are any procedures that are carried out as part of the trial, including activities to determine suitability for the trial
2. Diagnosed with type 2 diabetes mellitus
3. Treatment with up to 2 OADs (metformin, glitazone, SGLT-2 inhibitor, *alpha glucosidase inhibitor*, *glinide* or sulphonylurea),
4. Stable treatment with basal insulin ~~according to its label~~ (no requirement of minimum or maximum dose) for at least 90 days prior to screening, as judged by the investigator
5. HbA_{1c} 6.0-10.0% (both inclusive)
6. BMI ≥ 27 kg/m²
7. Age ≥ 18 years at the time of signing informed consent

2.2 Section 4.1 Objectives

Primary objective

To confirm superiority of liraglutide 3.0 mg vs. placebo, as an adjunct to a reduced-calorie diet and increased physical activity, on weight loss effectiveness in subjects with overweight or obesity and type 2 diabetes mellitus (T2DM) treated with a basal insulin and up to 2 oral antidiabetic (OAD) medications (metformin, glitazone, SGLT-2 inhibitor, *alpha glucosidase inhibitor*, *glinide* or sulphonylurea).

Secondary objectives

- To establish the effects of liraglutide 3.0 mg vs. placebo, as an adjunct to a reduced-calorie diet and increased physical activity, on relevant efficacy endpoints in subjects with overweight or obesity and T2DM treated with basal insulin and up to 2 OADs (metformin, glitazone, SGLT-2 inhibitor, *alpha glucosidase inhibitor*, *glinide* or sulphonylurea)
- To establish the safety and tolerability of liraglutide 3.0 mg vs. placebo, as an adjunct to a reduced-calorie diet and increased physical activity, in subjects with overweight or obesity and T2DM treated with basal insulin and up to 2 OADs (metformin, glitazone, SGLT-2 inhibitor, *alpha glucosidase inhibitor*, *glinide* or sulphonylurea)

2.3 Section 5.1 Type of trial

This is a 56-week randomised, double-blind, multi-national, multi-centre, placebo-controlled and two-armed trial in subjects with overweight or obesity and T2DM treated with basal insulin and up to 2 OADs (metformin, glitazone, SGLT-2 inhibitor, *alpha glucosidase inhibitor*, *glinide* or sulphonylurea).

2.4 Section 5.3.2.1 Oral antidiabetic medication

Any approved and marketed metformin, glitazone, SGLT-2 inhibitor, *alpha glucosidase inhibitor*, *glinide* or sulphonylurea product or combination products are allowed. Subjects treated with dipeptidyl peptidase-IV (DPP-IV) inhibitors are excluded from participating in the trial since DPP-IV inhibitors and GLP-1 receptor agonists should not be combined.

2.5 Section 5.3.2.2 Treatment with insulin throughout the trial

Any approved and marketed basal insulin (NPH insulin or insulin analogue) is allowed, at any dose, ~~if used according to its prescribing information at screening~~. Once-daily or twice-daily dosing is allowed, according to dosing schedule at baseline.

2.6 Section 6.2 Inclusion criteria

For an eligible subject, all inclusion criteria must be answered “yes”.

1. Informed consent obtained before any trial-related activities. Trial-related activities are any procedures that are carried out as part of the trial, including activities to determine suitability for the trial
2. Diagnosed with type 2 diabetes mellitus
3. Treatment with up to 2 OADs (metformin, glitazone, SGLT-2 inhibitor, *alpha glucosidase inhibitor*, *glinide* or sulphonylurea)
4. Stable treatment, at the discretion of the investigator, with any basal insulin ~~according to its label~~ (no requirement of minimum or maximum dose) for at least 90 days prior to screening
5. HbA_{1c} 6.0-10.0% (both inclusive)
6. BMI ≥ 27 kg/m²
7. Age ≥ 18 years at the time of signing informed consent
8. Maximum 5 kg self-reported weight loss within the past 90 days since screening
9. Increased physical activity is considered to be safe as judged by the investigator

Protocol Amendment no 3
Trial ID: NN8022-4272
UTN: U1111-1177-4903
EudraCT No.: 2015-005619-33

~~CONFIDENTIAL~~

Date:
Version:
Status:
Page:

19 February 2018
1.0
Final
1 of 8

Novo Nordisk

Protocol Amendment

no 3

**to Protocol, version 4.0
dated 14 September 2016**

Trial ID: NN8022-4272

SCALE™ Insulin

**Effect and safety of liraglutide 3.0 mg in subjects with overweight or obesity and type 2
diabetes mellitus treated with basal insulin**

Trial phase: 3b

Applicable to all countries

~~This confidential document is the property of Novo Nordisk. No unpublished information contained herein may be disclosed without prior written approval from Novo Nordisk. Access to this document must be restricted to relevant parties.~~

Table of Contents

1	Introduction including rationale for the protocol amendment.....	3
2	Changes	3
2.1	Section 1 Key secondary endpoints	3
2.2	Section 2 Flow chart.....	4
2.3	Section 4.2.2.1 Confirmatory secondary endpoints	5
2.4	Section 4.2.2.2 Supportive secondary endpoints	5
2.5	Section 8.4.4 Hypoglycaemic episodes	6
2.6	Section 8.5.2 Laboratory assessments for safety	6
2.7	Section 17.1 Sample size calculation	7
2.8	Section 17.4.1.1 Description of the testing procedure to address the effectiveness estimand for primary and confirmatory secondary endpoints	7

1 Introduction including rationale for the protocol amendment

Rationale for the changes:

- To reflect the outcome of the Impact of Weight on Quality of Life-Lite for Clinical Trials (IWQoL-Lite for CT) questionnaire validation and the recommendations from regulatory authorities to include the Short-form 36 (SF-36) questionnaire as a confirmatory secondary endpoint; the endpoint section and statistical hierarchy have been updated.
- Due to the low power to demonstrate a difference between active treatment and placebo, systolic blood pressure has been added as a supportive secondary endpoint and removed as a confirmatory secondary endpoint.
- Minor edits to Flow chart for clarity and accuracy.

In this protocol amendment:

- Any new text is written *in italics*.
- Any text deleted from the protocol is written using ~~strike through~~.

2 Changes

2.1 Section 1 Key secondary endpoints

Change from baseline to week 56 in:

- Waist circumference
- ~~Systolic blood pressure~~
- HbA_{1c}
- Fasting plasma glucose
- *Short Form-36 (SF-36) v2.0 acute, physical functioning score*
- Impact of Weight on Quality of Life-Lite for Clinical Trial Version (IWQoL-Lite for CT), ~~physical functioning~~ *physical function domain (5-items) score*
- ~~IWQoL-Lite for CT, mental/emotional functioning score~~

2.3 Section 4.2.2.1 Confirmatory secondary endpoints

Confirmatory secondary endpoints addressing the secondary efficacy objective:

- Proportion of subjects losing more than 10% of baseline body weight at week 56

Change from baseline to week 56 in:

- Waist circumference
- ~~Systolic blood pressure~~
- HbA_{1c}
- Fasting plasma glucose
- *Short Form-36 (SF-36) v2.0 acute, physical functioning score*
- *Impact of Weight on Quality of Life-Lite for Clinical Trial Version (IWQoL-Lite for CT), physical function domain (5-items) score*
- ~~IWQoL-Lite for CT, physical functioning score~~
- ~~IWQoL-Lite for CT, mental/emotional function score~~

2.4 Section 4.2.2.2 Supportive secondary endpoints

Supportive secondary efficacy endpoints

Change from baseline to week 56 in:

- Total daily basal insulin dose (% of pre-trial dose in U)
- Total daily basal insulin dose (U/kg)
- Total daily insulin dose (U)
- Total daily insulin dose (U/kg)
- 7-point self-measured plasma glucose (SMPG) profile, mean daytime glucose value
- *Systolic blood pressure*
- Diastolic blood pressure
- Lipids (total cholesterol [TC], low density lipoprotein cholesterol [LDL cholesterol], high density lipoprotein cholesterol [HDL cholesterol], very low density lipoprotein cholesterol [VLDL cholesterol], triglycerides [TG], free fatty acids [FFA])
- ~~Short Form-36 v2.0 acute (SF-36) (physical component summary (PCS), mental component summary (MCS) and subdomains)~~
- *SF-36 v.2.0 acute:*
 - *role-physical score*
 - *bodily pain score*
 - *general health score*
 - *vitality score*
 - *social functioning score*
 - *role-emotional score*
 - *mental health score*
 - *physical component summary (PCS)*

- *mental component summary (MCS)*
- *IWQoL-Lite for CT*
 - *pain/discomfort domain score*
 - *psychosocial domain score*
 - *total score*
- Weight related sign and symptom (WRSS) measure, total score

~~Proportion of subjects with the following at week 56:~~

~~Subjects who after 56 weeks achieve (yes/no):~~

- $HbA_{1c} < 7\%$ and weight loss $\geq 5\%$
- $HbA_{1c} < 7\%$, weight loss $\geq 5\%$ and no documented symptomatic hypoglycaemia
- ≥ 4.3 T-score points increase from baseline in SF-36 physical functioning score
- $\geq 2-3.8$ T-score points increase from baseline in SF-36 PCS
- $\geq 3-4.6$ T-score points increase from baseline in SF-36 MCS
- *Responder definition value for IWQoL-Lite for CT physical function domain (5-items) score*

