4.2.2.2 Supportive secondary endpoints

Supportive secondary efficacy endpoints

Change from baseline to week 56 in:

- Total daily basal insulin dose (% of pre-trial dose in U)
- Total daily basal insulin dose (U/kg)
- Total daily insulin dose (U)
- Total daily insulin dose (U/kg)
- 7-point self-measure plasma glucose (SMPG) profile, mean daytime glucose value
- Diastolic blood pressure
- Lipids (total cholesterol [TC], low density lipoprotein cholesterol [LDL cholesterol], high density lipoprotein cholesterol [HDL cholesterol], very low density lipoprotein cholesterol [VLDL cholesterol], triglycerides [TG], free fatty acids [FFA])
- Short Form-36 v2.0 acute (SF-36) (physical component summary (PCS), mental component summary (MCS) and subdomains)
- Weight related sign and symptom (WRSS) measure, total score

Proportion of subjects with the following at week 56:

- HbA_{1c} <7% and weight loss ≥5%
- HbA_{1c} <7%, weight loss ≥5% and no documented symptomatic hypoglycaemia
- ≥ 2 T-score points increase from baseline in SF-36 PCS
- ≥ 3 T-score points increase from baseline in SF-36 MCS

Supportive secondary safety endpoints

- Adverse events from randomisation until and including the follow-up visit
- Hypoglycaemic episodes until and including the follow-up visit

Change from baseline to week 56 in:

- Physical examination

Protocol
Trial ID: NN8022-4272
UTN: U1111-1177-4903
EudraCT no.: 2015-005619-33

~~CONFIDENTIAL~~

Date:	14 September 2016	Novo Nordisk
Version:	4.0	
Status:	Final	
Page:	24 of 123	

- Resting pulse
- ECG
- Laboratory measurements

5 Trial design

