6.5 Criteria for premature discontinuation of trial product

Efforts must be made so that subjects attend and complete all scheduled visit procedures. Subjects should stay in the trial regardless of adherence to randomised treatment, adherence to visit schedule or missing assessments. Only subjects who decline any further contact with the site in relation to the trial or withdraw consent are considered as withdrawn from the trial (see Section [6.6](#)).

The subject may be prematurely discontinued from trial product at the discretion of the investigator due to a safety concern.

The subject must be prematurely discontinued from trial product if the following applies:

1. Included in the trial in violation of any of the inclusion and/or exclusion criteria and/or randomisation criterion
2. Safety concern (not covered by any of below criteria) or unacceptable intolerability to trial product, as judged by the investigator
3. Hypersensitivity to trial product(s). If a hypersensitivity reaction occurs, discontinue trial product and other suspect medications
4. More than one episode of severe hypoglycaemia, or repeated episodes of documented symptomatic hypoglycaemia (ADA classification), despite lowering of insulin dose (as judged by investigator)
5. Pregnancy
6. Intention of becoming pregnant
7. Suspicion of pancreatitis (see Section [8.4.3.2](#) and [8.8.1](#))
8. Suspicion of acute gallstone disease (see Section [8.4.3.2](#) and [8.8.2](#))
9. Suspicion of drug-induced liver injury (DILI) (see Section [8.4.3.2](#) and [8.8.4](#))
10. Calcitonin ≥ 100 ng/L
11. Psychiatric disorder(s) that cannot be adequately treated with psycho- and/or pharmacotherapy (see Section [8.4.3.2](#), [8.6.5](#) and [8.8.5](#))
12. Initiation of anti-obesity medication and/or (plans for) weight loss surgery
13. Initiation of treatment with GLP-1 receptor agonist or DPP-IV inhibitors

14. Simultaneous participation in another clinical trial of an approved or non-approved investigational medicinal product

See Section [8.1](#) for procedures to be performed for subjects discontinuing trial product prematurely.

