8.4.4 Hypoglycaemic episodes

Plasma glucose should always be measured and recorded when a hypoglycaemic episode is suspected.

All plasma glucose values:

- ≤ 3.9 mmol/L (70 mg/dL) or,
- > 3.9 mmol/L (70 mg/dL) occurring in conjunction with hypoglycaemic symptoms

should be reported in the diary according to the instructions below throughout the trial from visit 1 to visit 25.

Upon onset of a hypoglycaemic episode the subject is recommended to measure plasma glucose every 15 minutes until the SMPG value is >3.9 mmol/L (70 mg/dL) and/or symptoms have been resolved in accordance with current guidelines³⁴.

A SMPG value ≤ 3.9 mmol/L (70 mg/dL) or hypoglycaemic symptoms must trigger a hypoglycaemic episode form to be completed by the subject. Repeated SMPG measurements and/or symptoms, occurring within a period of 60 minutes after onset on a hypoglycaemic episode, will by default be considered as one hypoglycaemic episode until a succeeding SMPG value is >3.9 mmol/L (70 mg/dL) and/or symptoms have been resolved and should be reported on one hypoglycaemic episode form. SMPG measurements ≤ 3.9 mmol/L (70 mg/dL) or hypoglycaemic symptoms after the 60 minutes period shall trigger the reporting of a new hypoglycaemia episode and prompt the subject to fill out a new hypoglycaemic episode form until a succeeding measurement is >3.9 mmol/L (70 mg/dL) and/or symptoms have been resolved.

In case of several low SMPG values within the 60 minutes interval, the lowest value is the one that will be reported as the SMPG value for the hypoglycaemic episode but the start time of the episode will remain as the time for the first SMPG value and/or symptom.

The record should include the following information:

- Start date and time of the hypoglycaemic episode
- The plasma glucose level before treating the episode (if available) and any follow up measurements.
- The lowest value measured during the hypoglycaemic episode will be reported as the plasma glucose value for the episode, the remaining values will be kept as source data in the diary.
- Whether the episode was symptomatic (Yes/No)
- A hypoglycaemic episode starting without symptoms should be updated to symptomatic if the subject experiences symptoms later during the episode.
- Whether the subject was able to treat him/herself

- If the severity of a hypoglycaemic episode aggravates, only one hypoglycaemic episode should be reported, reflecting the most severe degree of hypoglycaemia.

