The investigator must review the diary for low SMPG values not reported as hypoglycaemic episodes. The subject must be questioned whether any of the low values were severe, i.e., whether the subject was able to self-treat or not. If the subject was not able to self-treat, it has to be reported as a severe hypoglycaemic episode.

Low SMPG values for non-severe hypoglycaemic episodes not having a hypoglycaemic episode form completed within 7 days since the SMPG measurement should be reported on a hypoglycaemic episode form with as much information as possible. Novo Nordisk will not query for additional data except for the start date, SMPG value and whether the subject was able to self-treat due to decreased validity of such data^{36,39}.

The subject must be re-trained in how to report hypoglycaemic episodes if the investigator identifies low SMPG values not reported as hypoglycaemic episodes.

If the hypoglycaemic episode fulfils the criteria for a SAE, then an AE form and a safety information form (SIF) must also be filled in (see Section [12](#)).

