Nocturnal hypoglycaemic episodes: are episodes occurring between 00:01 and 05.59 both inclusive.

Hypoglycaemic episodes are classified according to the Novo Nordisk classification of hypoglycaemia (see [Figure 17-2](#)) and the ADA classification of hypoglycaemia (see [Figure 17-3](#)).

Novo Nordisk classification of hypoglycaemia

In normal physiology, symptoms of hypoglycaemia occur below a plasma glucose level of 3.1 mmol/L (56 mg/dL)²⁰ Therefore, Novo Nordisk has included hypoglycaemia with plasma glucose levels below this cut-off point in the definition of blood glucose (BG) confirmed hypoglycaemia.

Novo Nordisk uses the following classification (see [Figure 17-2](#)) in addition to the ADA classification:

Severe hypoglycaemia according to the ADA classification¹¹.

[figure not shown]
Symptomatic BG confirmed hypoglycaemia: An episode that is BG confirmed by plasma glucose value <3.1 mmol/L (56 mg/dL) **with** symptoms consistent with hypoglycaemia.

Asymptomatic BG confirmed hypoglycaemia: An episode that is BG confirmed by plasma glucose value <3.1 mmol/L (56 mg/dL) **without** symptoms consistent with hypoglycaemia.

Severe or BG confirmed symptomatic hypoglycaemia: An episode that is severe according to the ADA classification¹¹ or BG confirmed by a plasma glucose value <3.1 mmol/L (56 mg/dL) **with** symptoms consistent with hypoglycaemia.

BG confirmed hypoglycaemia: An episode that is BG confirmed by a plasma glucose value <3.1 mmol/L (56 mg/dL) **with** or **without** symptoms consistent with hypoglycaemia.

Severe or BG confirmed hypoglycaemia: An episode that is severe according to the ADA classification¹¹ or BG confirmed by a plasma glucose value <3.1 mmol/L (56 mg/dL) **with** or **without** symptoms consistent with hypoglycaemia.

Note: Glucose measurements are performed with capillary blood calibrated to plasma equivalent glucose values

Figure 17–2 Novo Nordisk classification of hypoglycaemia

ADA classification¹¹ of hypoglycaemia

[figure not shown]
Severe hypoglycaemia: An episode requiring assistance of another person to actively administer carbohydrate, glucagon, or take other corrective actions. Plasma glucose concentrations may not be available during an event, but neurological recovery following the return of plasma glucose to normal is considered sufficient evidence that the event was induced by a low plasma glucose concentration.

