Severe or BG confirmed hypoglycaemia: An episode that is severe according to the ADA classification¹¹ or BG confirmed by a plasma glucose value <3.1 mmol/L (56 mg/dL) **with** or **without** symptoms consistent with hypoglycaemia.

Note: Glucose measurements are performed with capillary blood calibrated to plasma equivalent glucose values

Figure 2–2 Novo Nordisk classification of hypoglycaemia

ADA classification¹¹ of hypoglycaemia

[figure not shown]
Severe hypoglycaemia: An episode requiring assistance of another person to actively administer carbohydrate, glucagon, or take other corrective actions. Plasma glucose concentrations may not be available during an event, but neurological recovery following the return of plasma glucose to normal is considered sufficient evidence that the event was induced by a low plasma glucose concentration.

Asymptomatic hypoglycaemia: An episode not accompanied by typical symptoms of hypoglycaemia, but with a measured plasma glucose concentration ≤ 3.9 mmol/L (70 mg/dL).

Documented symptomatic hypoglycaemia: An episode during which typical symptoms of hypoglycaemia are accompanied by a measured plasma glucose concentration ≤ 3.9 mmol/L (70 mg/dL).

Pseudo-hypoglycaemia: An episode during which the person with diabetes reports any of the typical symptoms of hypoglycaemia with a measured plasma glucose concentration > 3.9 mmol/L (70 mg/dL) but approaching that level.

Probable symptomatic hypoglycaemia: An episode during which symptoms of hypoglycaemia are not accompanied by a plasma glucose determination but that was presumably caused by a plasma glucose concentration ≤ 3.9 mmol/L (70 mg/dL).

Note: Glucose measurements are performed with capillary blood calibrated to plasma equivalent glucose values

Figure 2–3 ADA classification of hypoglycaemia

Physical examination

Outcome of the physical examination at screening and change in the physical examination category at week 56 will be summarised in tables.

Pulse

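### The composite of HbA1c, weight loss and hypoglycaemia does not name severe hypoglycaemia, so a subject with severe episodes can count as a responder

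*Protocol*

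**What the plan says.** Protocol 4.2.2.2 lists a responder endpoint at week 56 that requires HbA1c below 7%, "weight loss ≥5% and no documented symptomatic hypoglycaemia". Amendment 3 (its section 2.4) edits neighbouring items in that list and leaves the hypoglycaemia component, "and no documented symptomatic hypoglycaemia", unchanged. SAP 2.4.3.1 refers back to the protocol list and says only that proportions are analysed by logistic regression. Neither document gives a derivation rule for the hypoglycaemia component.

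The ADA classes are defined in Protocol 17.4.2.2 and again in SAP 2.4.3.2. Severe hypoglycaemia is "An episode requiring assistance of another person to actively administer carbohydrate, glucagon, or take other corrective actions". For that class the text accepts that "Plasma glucose concentrations may not be available during an event". Documented symptomatic hypoglycaemia is "An episode during which typical symptoms of hypoglycaemia are accompanied by a measured plasma glucose concentration" of 3.9 mmol/L or lower.

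**The concern.** A composite of this kind will be read as benefit achieved without troublesome hypoglycaemia. Protocol 18.1 treats hypoglycaemia as a recognised risk when liraglutide is combined with other glucose-lowering drugs, and every subject here takes basal insulin. The component screens for one ADA class and does not mention the most serious one. The wording also leaves open whether a severe episode with a low glucose value counts, so two programmers could derive the endpoint differently from the same data. At stake are the meaning and reproducibility of one supportive proportion. The primary and confirmatory results are not affected.

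**Working it through.** The documents state no expected proportion, power or rate for this endpoint, so there is no figure to reproduce. The check compares the definitions and then traces one subject through the plan.

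**Step 1: which episodes fail the component.** The text allows two readings. In the first, the classes may overlap and each definition is applied literally. In the second, each episode belongs to one class only.

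| Episode | Classes may overlap | Classes exclusive |
|---|---|---|
| Not severe, symptoms, measured glucose 3.9 mmol/L or lower | fails the component | fails the component |
| Severe, symptoms, measured glucose 3.9 mmol/L or lower | fails the component | does not fail it |
| Severe, no measured glucose | does not fail it | does not fail it |

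The last row is the same under both readings.

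**Step 2: which reading the text favours.** Three places point towards exclusive classes.
- Protocol 8.4.4 says that when an episode worsens, "only one hypoglycaemic episode should be reported, reflecting the most severe degree of hypoglycaemia".
- Criterion 4 of Protocol 6.5 names the two classes side by side: "More than one episode of severe hypoglycaemia, or repeated episodes of documented symptomatic hypoglycaemia (ADA classification".
- The sponsor's own classification (Protocol 17.4.2.2, SAP 2.4.3.2) joins severe to a glucose-confirmed class explicitly when both are meant. The composite has no such addition.

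None of these settles the matter. They make the exclusive reading the more likely one.

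**Step 3: the path to a counted success.**
1. A subject has severe episodes and no other episode that is documented symptomatic.
2. Trial product may be stopped under criterion 4. Protocol 6.5 and 8.1 keep the subject in the trial.
3. If the subject attends at week 56, SAP Table 2-1 classes the assessment as an available drop-out, so it is used.
4. SAP 2.4.3.1 places supportive endpoints under the effectiveness estimand, which SAP Section 2 defines irrespective of adherence.
5. No rule makes a severe episode, or stopping because of one, a failure. With HbA1c below 7% and weight loss of at least 5%, the subject is a responder.

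**Step 4: scale.** SAP 2.1 plans 200 subjects per arm, so one such subject moves the arm's proportion by 1/200 = 0.5 percentage points. The documents give no severe-episode rate. As an assumption, let 1% to 3% of an arm have severe but no documented symptomatic episodes:
- 1%: 200 × 0.01 = 2 subjects; 2 × 0.5 = 1 percentage point.
- 3%: 200 × 0.03 = 6 subjects; 6 × 0.5 = 3 percentage points.

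These are ceilings. They are reached only if every such subject also meets both the HbA1c and the weight criterion. The effect on the comparison between arms depends on how the affected subjects split between them, which is unknown.

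**Step 5: the period.** No text says whether the component covers the whole trial, time on drug only, or a window near week 56. For a subject off drug for months, this choice alone can decide responder status.

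**The case against.** The strongest defence is that the endpoint's label names exactly the class it counts, and no passage says that it is meant to show freedom from all hypoglycaemia. It is supportive and outside the hierarchy in SAP Table 2-6. Protocol 4.2.2.1 limits disclosure to primary and confirmatory endpoints. Severe episodes are summarised in their own right, both on drug and in trial (SAP 2.4.3.2). Protocol 8.4.4 also asks for glucose to be measured whenever an episode is suspected, and Protocol 6.3 excludes known hypoglycaemia unawareness and recurrent severe episodes. Both reduce the number of severe episodes that escape. All of this stands and keeps the consequence small. It does not close the gap, because a severe episode without a value passes on either reading.

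A reader might also infer more than the documents support:
- *That the endpoint ignores every severe episode.* This is not shown. The ADA classification figures were missing from the text available for this review, and the written definition of documented symptomatic does not exclude a severe episode with symptoms and a low value.
- *That two severe episodes always end treatment.* Criterion 4 adds the condition that the episodes occur despite a lowered insulin dose, in the investigator's judgement, and this may govern both parts of the criterion.
- *That late diary entries are a second flaw.* For non-severe low values without a form within 7 days, Protocol 8.4.4 says the sponsor "will not query for additional data except for the start date, SMPG value and whether the subject was able to self-treat". The same paragraph still asks for the form to be as complete as possible and gives reduced data validity as the reason for limiting queries. Symptom status may be missing for some values, but the rule is not an error.
- *That a number of false successes can be calculated.* That would need a severe-episode rate and an HbA1c response rate that the documents do not give. It would also need to remove subjects who had a documented symptomatic episode as well, since they already fail.

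**Conclusion.** The point holds as a defect of definition. Followed as written, the plan can count a subject with severe hypoglycaemia as a success on the composite. This is certain for severe episodes without a measured glucose and likely for all severe episodes if the classes are programmed as exclusive. In either case the subject must have no other documented symptomatic episode. The numerical effect is probably small, at 0.5 percentage points of an arm per subject. The 1 to 3 point ceiling rests on an assumed rate. The change is still worth making, because the endpoint is open to misreading and the correction needs no new data.

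**What to change.** In Protocol 4.2.2.2 and in the SAP derivation, define the third component as *no severe and no documented symptomatic hypoglycaemia (ADA)*. Take severe status from the self-treatment item that Protocol 8.4.4 already collects. State the period over which episodes count: the whole trial, on drug, or another named window. Optionally, add one supportive run that counts glucose values of 3.9 mmol/L or lower with unknown symptom status as events, to show how far the result depends on them.

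The cost is one phrase in the endpoint list, one derivation rule and one stated period. The success proportion can only stay the same or fall slightly when severe episodes are added.
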